# Independent variable

Variable	Conceptual definition	Operational definition	Туре	Measurement scale (years)	
Age	Time elapsed from the birth of a person to a certain moment.	The age recorded in the clinical record at the patient's admission to the hospital will be considered.	Discrete quantitative	
 
18 a 27
 
28 a 37
 
38 a 47
 
48 a 57
 
58 a 67
 
68 a 77
 
78 a 87
 
88 a 97
 
997
 
	
Gender	Social concepts of functions, behaviors, activities and attributes for men and women.	Gender that is registered in the clinical record	Qualitative nominal	Male Female	
Prone position	What is called the prone position	Record in the record of the placement of the patient in the prone position for a minimum of 2 hours.	Qualitative	Nominal (dichotomous): Yes No	
Type of oxygen support supplied	Device used for supplemental oxygen administration.	Record in the clinical record of the type of oxygen supplied.	Qualitative nominal	
 
Nasal cannulas
 
High flow nasal cannulas
 
Face mask
 
Other
 
	
Partial oxygen saturation index (SpO2) / inspired oxygen fraction (FiO2)	Resulting index for SpO2 / FiO2 ratio	2 index records will be taken at admission and the second after the patient's prone position, recorded in the clinical record.	Discrete quantitative	1. 100 a 150 2. 151 a 200 3. 201 a 250 4. 251 a 300 5. 301 a 350	

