Awake prone positioning and oxygen therapy in patients with COVID-19 (APRONOX)

*Prospective, observational, multicenter study.* 

Identifiers: NCT04407468 Unique Protocol ID: 1178/SESEQ-HSGJR/08-05- 20/UTI Date: 10/05/2020

APRONOX trial is a retrospective, observational, multicenter study that consists of the main objective, which is to observe the impact of the awake prone, and to see how many patients required intubation, with the additional objectives described in this research

By the APRONOX group

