# **Specific objectives**

To explore the impact of the awaken prone positioning on the partial oxygen saturation / inspired oxygen fraction index (SaO2 / FiO2).

Determine the free hours without the need for orotracheal intubation of patients in the awaken prone positioning.

To describe the characteristics of the patients in need of orotracheal intubation who were in the awaken prone positioning and those who were not.

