#### **Inclusion criteria**

Patient's records with the following characteristics:

- Patients over 18 years of age
- Patients of both genders
- Patients diagnosed with COVID-19 infection
- Patients admitted to hospital
- Complete file

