#### Variables categorization

The source of collection of the variables will be the clinical file.

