#### Dependent

Variable	Conceptual definition	Operational definition	Туре	Measurement scale
Orotracheal intubation	Placing a probe into the trachea through the mouth or nose to connect to a mechanical ventilator.	Performing intubation for any cause or non- intubation during your hospitalization.	Qualitative	Nominal (dichotomous): Yes No

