#### Statistical analysis

Descriptive statistics, measures of central tendency, measures of dispersion and standard deviation will be used.

While for the qualitative variable's frequency measures (relative, absolute and percentage) were used. Relative risk will be performed with a 95% confidence interval of significance (95% CI) and contingency tables.

For inferential statistics, the difference in proportions between the dependent (orotracheal intubation) and independent (prone position) variables will first be verified based on the number of expected observations (<5) Fisher's exact test or (> 5) Chi square test, contrasting H0:  $\phi = 1$ , taking p <0.05 as a statistically significant value.

A multivariate analysis will be used to generate linear regression models with the different variables: prone time, age, gender and orotracheal intubation, SpO2 / FiO2 index in order to explain their interactions (if the time in prone, age or gender affects the main objective) as well as adopting the best model that matches the observations (best R2, AIC) as a predictive model.

The results will be presented in graphs and / or tables as appropriate.

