#### Information gathering instrument

Case	Gender	Age	Comorbidities	Type of oxygen support supplied	Pharmacotherapy	Awake prone position (Yes/no)	Time of Awake prone position (hours)	Initial SaO2/FiO2	SaO2/FiO2 before to the prone position	Prone position (hours)	Intubation Yes/No

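### Prone and not-prone patients share no time zero and the form records no event times, so the relative risk is biased as a measure of awake proning's impact, in an unknown net direction

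*Protocol*

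**What the plan says.** - **Exposure** (Protocol, Independent variable). Prone is Yes or No, and Yes means "Record in the record of the placement of the patient in the prone position for a minimum of 2 hours". The definition gives no start, no time window and no limit to proning while awake or before intubation.
- **Outcome** (Dependent). Intubation is Yes or No: "Performing intubation for any cause or non- intubation during your hospitalization".
- **Eligibility** (Inclusion, Exclusion and Elimination criteria). Adults with COVID-19 and a complete file qualify if they are "Patients admitted to hospital". Nothing requires them to be un-intubated or on oxygen at a stated moment.
- **Analysis** (Statistical analysis). "Relative risk will be performed with a 95% confidence interval of significance (95% CI) and contingency tables", with a chi-square or Fisher test. Linear regression models that include prone time, age, gender and the SpO2/FiO2 index follow.
- **Data** (Information gathering instrument). One column begins "Awake prone position (Yes/no". Two others hold prone hours, and intubation is Yes/No. No column holds a date or time of admission, prone start, intubation or end of stay.
- **Purpose.** The title page says the study is "to observe the impact of the awake prone". A specific objective is "Determine the free hours without the need for orotracheal intubation of patients in the awaken prone positioning".

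**The concern.** Three features of the definitions distort the comparison even if proning does nothing.

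1. **Immortal time.** To count as awake prone, a patient must stay un-intubated until two hours prone are complete. Anyone intubated on arrival, or before that point, enters the not-prone group as a certain event. This pushes the RR below 1.
2. **Patients never at risk.** Admitted patients who never needed oxygen would sit in the not-prone group with almost no events. This pushes the RR above 1.
3. **Proning on the ventilator.** The variable definition does not say awake, although the form does. If the definition governs, patients proned only after intubation are coded Yes, each with an event. This also pushes the RR above 1.

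An RR below, above or near 1 could therefore arise with no effect of proning. A larger sample would not help, because the error lies in the classification. Without event times, the form can neither correct this nor deliver the intubation-free hours objective.

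**Working it through.** **Sample size used.** The Protocol's own figure reproduces: 8463 × 1.96² × 0.25 / (8462 × 0.05² + 1.96² × 0.25) = 8127.87 / 22.1154 = 367.5, rounded up to 368.

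**Assumptions.** The Protocol plans no intubation risk, proning share or timing. The illustration assumes no prone effect and proning independent of prognosis. Intubation risk among at-risk patients is r = 0.36, which happens to be the complement of the 64% who avoided intubation in an emergency-department series cited in the Theoretical framework. The share who would be proned is c = 0.60. Times to intubation (mean μT) and to prone start (mean μS) are exponential, and two hours are needed to qualify.

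**Immortal time alone.** The chance that a patient destined for both completes two prone hours before intubation is

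q = exp(−2/μT) × μT/(μT + μS)

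- Risk if prone = rcq / [rcq + (1 − r)c]
- Risk if not prone = r(1 − cq) / [r(1 − cq) + (1 − r)(1 − c)]

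| μT / μS (h) | q | Risk if prone | Risk if not prone | RR | False rejection, n = 368 |
|---|---|---|---|---|---|
| 96 / 6 | 0.9218 | 0.1991/0.5831 = 34.1% | 0.1609/0.4169 = 38.6% | 0.88 | 14–15% |
| 48 / 12 | 0.7674 | 0.1657/0.5497 = 30.1% | 0.1943/0.4503 = 43.1% | 0.70 | 72–75% |
| 24 / 24 | 0.4600 | 0.0994/0.4834 = 20.6% | 0.2606/0.5166 = 50.4% | 0.41 | 100% |

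The rejection rates come from simulated chi-square tests.

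If early intubations are less frequent (gamma times, shape 2), the RR is about 0.97, 0.82 and 0.46, with rejection about 5%, 31% and 100%. Over 20–50% intubated, 40–60% proned and both time models, the RR runs from 0.33 to 0.99. Early proning with late intubation can therefore leave almost no bias.

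**Adding the opposing mechanisms** (exponential times, rows in the same order):

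- *Never on oxygen, 10–20% of the cohort.* This adds 0.1111 to 0.25 non-events per at-risk patient to the not-prone group. For 96/6, 0.3415 / (0.1609/0.5280) = 1.12 and 0.3415 / (0.1609/0.6669) = 1.42. All three cases: 1.12–1.42, 0.87–1.09 and 0.50–0.60.
- *5% intubated on arrival plus 15% never on oxygen.* This adds 0.05/0.80 = 0.0625 events and 0.15/0.80 = 0.1875 non-events to the not-prone group. For 96/6, the not-prone risk is 0.2234/0.6669 = 33.5%. RR: 1.02, 0.82 and 0.49. Rejection: 5–6%, 26% and 99%.
- *30% of intubated patients not already prone recoded Yes, with no other addition.* For 96/6, 0.0483 moves across, giving 0.2474/0.6314 = 39.2% against 0.1126/0.3686 = 30.6%. RR: 1.28, 1.06 and 0.76.

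**Checking the repair.** Simulate all three mechanisms together (5% on arrival, 15% never on oxygen, 30% proned on the ventilator). Then restrict to at-risk patients un-intubated at a 12 h or 24 h landmark and classify exposure at that hour. The RR is 0.996–1.004 and rejection 4.7–5.2% in all three timing cases. The share of at-risk patients kept is 1 − 0.36 × (1 − exp(−L/μT)): 86–96% at L = 12 h and 77–92% at L = 24 h.

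**The case against.** - **The population and exposure are implied.** The title mentions oxygen therapy, the device list has no category for none, the SpO2/FiO2 scale ends at 350, and the objectives and form say awake. On that reading only immortal time remains, and the bias runs one way. This is a fair reading of intent, but no criterion states it and the variable definition omits awake. The never-oxygen and ventilator-prone shares used above are assumptions.
- **The bias may be small.** The Protocol's background favours early proning. If intubation also comes late, the RR is 0.88–0.97 and false rejection 5–15%. This stands, but nothing in the Protocol shows that intubations were late.
- **It tests only a relationship.** The question, hypotheses and main objective are so worded, and the crude test addresses that. The criticism applies to the impact reading, which the title page invites.
- **Later analysis could handle it.** The planned regression uses prone time, which for awake proning is itself cut short by intubation. A separate SAP could choose better models but could not analyse times the form does not collect. The two prone-hours columns read as durations; even if one gave time to prone start, intubation and end of stay would still be undated.
- **A landmark dilutes a real effect.** At 12 h about 19%, 42% and 63% of eventually proned patients still at risk are coded not prone. A true RR of 0.5 reads about 0.55–0.58. This stands as a cost. A time-dependent exposure avoids it, but was not simulated here.

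**Conclusion.** The concern holds. The misclassification follows from the stated definitions whenever some patients are intubated before completing two prone hours, and the collection form leaves no means of correcting it. Its size cannot be known from the Protocol: immortal time alone gives an RR from 0.33 to 0.99 under no effect, and the eligibility and wording gaps can move the RR above 1. The net direction is undetermined on the criteria as written. All these figures rest on assumed risks, shares and timings, with proning independent of prognosis. Confounding by severity is a further, separate source of error. The fault sits in the main comparison and should be corrected before the result is read as the impact of awake proning.

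**What to change.** 1. State a time zero, and restrict the analysis to patients who are un-intubated and on supplemental oxygen at that point.
2. Align the prone definition with the form, so that exposure counts only if it is awake and before intubation.
3. Add four date/time columns: time zero, first prone session, intubation and end of stay. The Protocol already says "The source of collection of the variables will be the clinical file", so these come from files being read anyway.
4. Make the main comparison either a landmark analysis at a prespecified hour or a model with prone as a time-dependent exposure. The same columns then serve the intubation-free hours objective.

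The cost is extra abstraction, amended wording, a narrower population than all COVID-19 admissions, and fewer patients at a landmark, in the proportions shown above. A landmark also carries the dilution noted above. Some files may lack exact clock times. The change removes the timing bias only; adjustment for severity is still needed.

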# Identifiers: NCT04407468 Unique Protocol ID: 1178/SESEQ-HSGJR/08-05- 20/UTI

# Theoretical framework

The prone position strategy for patients with acute respiratory distress syndrome (ARDS) is simple and cost-effective since the first description on its use in patients with acute respiratory failure to improve hypoxemia. Different studies have looked for its safety and efficacy in various clinical scenarios, demonstrating that its early use in combination with non-invasive mechanical ventilation (NIV) or high-flow oxygen therapy can reduce intubation rate and mortality in ARDS. In the COVID-19 pandemic, high-value medicine and resource optimization are critical.

Scaravilli et al (1) carried out an analysis of 15 patients admitted presenting acute hypoxemic respiratory failure with spontaneous breathing undergoing a prone position, finding that the strategy had no deleterious effects on PaCO2, pH, respiratory rate, or hemodynamics. For their part, Valter et al (2) reported four cases of patients with respiratory failure where a prone position strategy was used, showing an improvement in oxygenation and good tolerance while awake, avoiding the need for intubation in these patients without significant complications (2).

Ding et al (3) recently published a prospective cohort study of patients with moderate to severe grade ARDS using the prone position combined with non-invasive mechanical ventilation (NIV) or high flow nasal cannula (HFNC), demonstrating the safety and efficiency of the maneuver, finding an improvement in oxygenation and a decrease in the need for intubation. Pérez et al (4) reported a case series of patients with severe non-infectious ARDS where the strategy of early prone and HFNC or NIV, for 2 to 3 hours, improved oxygenation and intubation was avoided in 5 of the 6 cases studied.

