#### Justification

COVID-19 is a pandemic that has significantly challenged health systems worldwide. Due to the large number of infections around the world, the implementation of strategies to reduce the number of intubations and the need for invasive mechanical ventilation becomes important. In addition to the inability of the Mexican health system to respond, patients under invasive ventilation have not had a favorable survival outcome. Up to 97% mortality has been reported in patients requiring intubation. The exact cause of this poor prognosis is not yet known. Early recognition of hypoxemic patients could help with the results. It seems reasonable in these patients to perform procedures to improve the clinical respiratory picture before intubation in less severe cases due to the quoted above. Prone patient placement during invasive mechanical ventilation is a widespread practice in the management of severe ARDS of other etiologies. Currently, few attempts have been made to implement the prone position in patients who spontaneously ventilate with supplemental oxygen, high-flow nasal cannulas, or noninvasive mechanical ventilation. Taking into account that it is a procedure that does not require additional infrastructure within the services and does not represent an additional cost for its implementation, it becomes a valuable tool in the context of COVID-19 where intubation is associated with high mortality, additionally there are mechanical ventilator deficits in most hospitals. This work has feasibility to be carried out because it will be carried out in critical areas that have equipment and trained personnel for it in the different shifts, in addition to having patients diagnosed with COVID-19.

**Null hypothesis (H0):** In patients diagnosed with COVID-19 infection, there is no relationship between the awaken prone positioning and orotracheal intubation.

Alternate hypothesis (H1): In patients diagnosed with COVID-19 infection, there is a relationship between the awaken prone positioning and the need for orotracheal intubation.

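### The oxygen-support variable has no level for non-invasive ventilation, no time point and no place in the listed model

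*Protocol*

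**What the plan says.** The Independent variable table of the Protocol defines the oxygen-support variable as "Device used for supplemental oxygen administration". Its operational definition is "Record in the clinical record of the type of oxygen supplied". The scale opens with nasal cannulas and continues "High flow nasal cannulas Face mask Other". There is no level for non-invasive ventilation and none for a patient on room air. No time point is given. In the same table, age and the first SpO2/FiO2 reading are both tied to admission.

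The rationale gives non-invasive ventilation and high-flow oxygen equal standing. The Theoretical framework opens by saying of proning that "its early use in combination with non-invasive mechanical ventilation (NIV) or high-flow oxygen therapy can reduce intubation rate and mortality in ARDS". The Justification says that "few attempts have been made to implement the prone position in patients who spontaneously ventilate with supplemental oxygen, high-flow nasal cannulas, or noninvasive mechanical ventilation". The framework also notes that awake proning can be done on atmospheric air.

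Eligibility sets no limit on respiratory support. The relevant inclusion criterion is simply "Patients admitted to hospital", and the exclusion and elimination criteria name no device.

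Under Statistical analysis, the regression models are to be built "with the different variables: prone time, age, gender and orotracheal intubation, SpO2 / FiO2 index". Oxygen support is not in that list, nor in the table of confounding variables, which holds comorbidities and pharmacotherapy. The data-collection form has one undated column for type of oxygen support.

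**The concern.** This is a non-randomised comparison of intubation between patients who were and were not proned. The support a patient was receiving can plausibly influence both whether staff proned them and whether they were later intubated, so it is a natural baseline confounder. Three features limit its use here.

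- **Coding.** A patient on non-invasive ventilation shares a code with unlike patients, so this group cannot be described or adjusted for from the codes.
- **Timing.** Intubation is assessed over the whole hospital stay, and support may be stepped up during it. One undated entry may therefore reflect a device used after proning. Adjusting for that would mean conditioning on something the exposure may have changed.
- **Use.** The variable is collected but not listed for adjustment.

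At stake are how well the prone estimate is adjusted for respiratory severity, and whether proning combined with non-invasive ventilation can be described at all. A later analysis plan could add a model term, but it could not supply a code or a time point that data collection never captured.

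**Working it through.** **1. Does the rationale rest on non-invasive ventilation?** The Theoretical framework describes nine awake-prone studies, seven reported and two in progress. Three of the nine are described with non-invasive ventilation, each time as an alternative to high-flow oxygen. Two more are described with high-flow oxygen only, and four name neither. So the rationale rests on it in part. High-flow oxygen has its own code; its partner in those three studies does not.

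**2. Where would such a patient be coded?** The Protocol gives no rule. 'Other' is the natural choice; 'Face mask' is possible when ventilation is delivered by mask. Either way the code does not identify the patient. A room-air patient has no natural code, because the variable is defined as a device.

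**3. What severity adjustment remains?** The listed model contains the SpO2/FiO2 index, without saying which of the two readings. The admission reading can serve as a baseline. Its bands run from 100 to 350:

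- On room air (FiO2 0.21), an index of 350 corresponds to SpO2 = 350 × 0.21 = 73.5%. Any room-air patient saturating above that is off the top of the scale.
- At FiO2 1.0, the index equals SpO2 in per cent, so any saturation below 100% is off the bottom.

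As banded, the index has no category at either extreme of support. If the raw values on the form are analysed, this gap largely closes.

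**4. Can the bias be sized?** No. The document gives no device shares and no risks by device. An illustration with assumed values shows how open the answer is. Take a category that mixes non-invasive ventilation (risk r1) with other patients (risk r0), and let proning have no effect. If the share on non-invasive ventilation is a among proned and b among unproned patients, then

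RR = [a·r1 + (1 − a)·r0] / [b·r1 + (1 − b)·r0].

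| a | b | RR if r1 = 0.60, r0 = 0.20 | RR if r1 = 0.50, r0 = 0.30 |
|---|---|---|---|
| 0.30 | 0.50 | 0.32/0.40 = 0.80 | 0.36/0.40 = 0.90 |
| 0.40 | 0.40 | 0.36/0.36 = 1.00 | 0.38/0.38 = 1.00 |
| 0.50 | 0.30 | 0.40/0.32 = 1.25 | 0.40/0.36 = 1.11 |
| 0.70 | 0.30 | 0.48/0.32 = 1.50 | 0.44/0.36 = 1.22 |

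The bias can go either way, and it vanishes when use of non-invasive ventilation does not differ by prone status. These ratios apply inside one device category, which the plan does not analyse separately. They show why adding the device to the model with its present codes would leave some mixing. They do not estimate bias in any planned result.

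**5. Sample size and numbers affected.** The stated figure reproduces:

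n = 8463 × 1.96² × 0.25 / (8462 × 0.05² + 1.96² × 0.25) = 8127.87 / 22.1154 = 367.5, rounded up to 368.

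No device category enters this formula, so new levels leave it unchanged. If 1%, 5%, 10% or 20% of 368 patients were on non-invasive ventilation (assumed shares), that would be about 4, 18, 37 or 74 patients. At the low end the level would have to be merged for modelling.

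**The case against.** The strongest reply is that nothing planned depends on this variable. The main comparison is a crude relative risk with a chi-square or Fisher test, and the listed regression does not contain device type, so a new code alone changes no planned estimate. Severity is also not ignored: the SpO2/FiO2 index is recorded at admission, is named in the model, and partly reflects support intensity because FiO2 is its denominator. All of this stands. It is why the remedy needs the code, the time point and the model term together, and why the point is a small one.

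Several stronger readings are tempting but unsupported:

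- *Non-invasive ventilation is one of three supports under study.* The Justification's list, "patients who spontaneously ventilate with supplemental oxygen, high-flow nasal cannulas, or noninvasive mechanical ventilation", describes settings of earlier attempts at proning. The objectives and eligibility criteria define no studied supports.
- *Severity cannot be separated.* It can in part, through admission SpO2/FiO2.
- *High-risk patients are known to be pooled in 'Other'.* That placement is inferred, and no figure in the document shows their risk.
- *The prone estimate is inflated by some stated ratio, such as 1.50.* That value depends wholly on assumed inputs.
- *Proning by oxygen therapy cannot be described.* Four levels can still be tabulated by prone status; it is the non-invasive ventilation and room-air groups that lack their own.
- *The loss is permanent.* The data come from clinical files that can be reopened, and the form prints no codes in this column, so device names may in fact be written down.

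**Conclusion.** The concern holds as a minor, inexpensive defect in measurement and adjustment. The scale omits a support on which the rationale partly rests and which eligibility admits, the entry is undated, and the variable is absent from the listed adjustment. Admission SpO2/FiO2 is therefore the only listed baseline measure of respiratory severity, and its bands do not cover the extremes of support.

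No numerical size can be given. Any residual confounding could move the relative risk up or down, or not at all, depending on whether device use differs by prone status after adjustment for the index. The conclusion assumes that some enrolled patients receive non-invasive ventilation, which the criteria allow but the document does not quantify. It also assumes that an adjusted model for intubation is intended. The Protocol lists intubation among the regression variables without stating its role there.

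**What to change.** Make three linked changes to the Protocol and form.

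1. Add 'Non-invasive ventilation' and 'Room air/none' as levels, keep 'Other' for the remainder, and state that ventilation delivered by mask is not coded as face mask.
2. Record the device at admission for every patient, the same time point as the first SpO2/FiO2 reading.
3. Add this baseline device to the adjusted intubation model beside admission SpO2/FiO2, with a stated rule for merging sparse levels.

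The common time point matters. Taking the device just before proning in proned patients but at admission in the others would measure severity at different moments by exposure group and could add a bias of its own. The price of using admission is that deterioration between admission and proning is not captured.

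The cost is two more codes and, with six levels, up to 6 − 1 = 5 model degrees of freedom, fewer after merging. The planned 368 patients are unaffected. Files already extracted would need to be re-read for this one item.

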#### Methodology

Study type: Observational, retrospective cohort study.

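### The variable definition takes the second SpO2/FiO2 reading after prone, but the data form labels its second index column as before prone, so the form has no place for a post-prone value

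*Protocol*

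**What the plan says.** Three parts of the Protocol bear on when the oxygenation index is measured.

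- **Specific objectives.** One objective is "To explore the impact of the awaken prone positioning on the partial oxygen saturation" to FiO2 index.
- **Independent variable table, SpO2/FiO2 row.** The operational definition reads "2 index records will be taken at admission and the second after", and goes on to name the patient's prone position as the event that the second reading follows.
- **Information gathering instrument.** The form carries the index in two columns, "Initial SaO2/FiO2" and, next to it, "SaO2/FiO2 before to the prone position".

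Two further statements set the context. The design is given under Methodology as "Observational, retrospective cohort study", and Variables categorization says "The source of collection of the variables will be the clinical file". The Statistical analysis section also lists the index among the regression variables ("SpO2 / FiO2 index in order to explain their interactions") without saying which of the two readings is meant.

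**The concern.** The definition and the form put the second reading on opposite sides of the exposure. An effect of prone on oxygenation needs a value taken after prone to set against one taken before. As printed, the form asks for two values that both precede prone. Their difference describes how the patient changed between admission and being turned, and says nothing about the effect of turning.

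There is a second risk. The study is multicenter. If some abstractors follow the header and others follow the definition, the second index column will mix pre-prone and post-prone values. The form could not reveal this, because no column records when an index reading was taken.

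At stake are the specific objective on the index and any regression that uses the second reading. The comparison of intubation between proned and non-proned patients does not use this column.

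**Working it through.** No figure stated in the Protocol bears on this point, and the sample size of 368 does not depend on it. The check sets the definition against the form's header.

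**Step 1. Count the form's columns, left to right.**

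| Columns | Content |
|---|---|
| 1 to 6 | Case, gender, age, comorbidities, oxygen support, drug treatment |
| 7 | Awake prone, yes or no |
| 8 | "Time of Awake prone position (hours") |
| 9 | "Initial SaO2/FiO2" |
| 10 | "SaO2/FiO2 before to the prone position" |
| 11 | A second prone column, in hours |
| 12 | Intubation, yes or no |

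Total columns: 6 + 6 = 12. Index columns: 2 (columns 9 and 10). Index columns labelled after or during prone: 0.

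**Step 2. Match the defined readings to the columns.**

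| Reading in the Independent variable table | Column on the form |
|---|---|
| At admission | Column 9 |
| After prone | None |

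Matched: 1 of 2. Column 10 holds a before-prone reading that the definition does not ask for.

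**Step 3. See whether another field could supply or identify the missing value.** Columns 8 and 11 concern prone and are expressed in hours; neither says when an index reading was taken. Columns giving the date or clock time of an index reading: 0. No other section of the Protocol provides a place to record a post-prone value.

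**Step 4. Work out what the printed form can estimate.** For a proned patient, column 10 minus column 9 is the index before prone minus the index at admission. Both terms precede the exposure, so the difference contains no effect of prone. A never-proned patient has no post-prone value to lose, so the gap concerns proned patients only.

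**Step 5. Size.** The Protocol gives neither the number nor the proportion of patients proned. The number of files that would need a second look cannot be derived, and no estimate is made.

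**Side observation.** The index is named with SaO2 in Specific objectives and on the form, and with SpO2 in the Independent variable table and Statistical analysis. This is a labelling inconsistency with no bearing on timing, and the conclusion does not rest on it.

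**The case against.** The strongest reply is that this is one mistranslated word. The English is visibly translated throughout, the operational definition is clear, and the specific objective agrees with it. Column 10 also follows the columns recording whether and how long the patient was proned, which suits an after-prone reading. An abstractor who works from the definition would enter the right value. Mixed data are a possibility, and nothing in the Protocol shows that it occurred. The objective is exploratory, the values can be retrieved from the clinical files, and the main comparison is untouched. A time stamp is also more than the definition requires, since it fixes the reading by its relation to prone and not by the clock.

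Much of this stands. A slip is plausible, the mixing of values is conditional on how sites read the header, and a correct header would meet the definition without a time field. It does not remove the contradiction. The form is the instrument on which the data are captured, its header is legible and also makes sense as a true pre-prone baseline, and nothing in the Protocol tells the abstractor which section prevails. Nor could a statistical analysis plan repair it, because no analysis can use a value that the form did not collect.

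**Conclusion.** The concern holds. The Independent variable table and the Information gathering instrument contradict each other on the timing of the second index reading. Filled in as printed, the form holds no post-prone value for any proned patient, and the specific objective on the index cannot be answered without returning to the clinical files.

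This should be fixed, but its reach is limited. It affects proned patients, one specific objective and any model that uses the second reading. It does not affect the main intubation comparison. The loss is recoverable to the extent that the clinical files hold a post-prone value. Confidence is high for the mismatch in the text. The mixing of values across sites is a possibility only, and the number of files affected is unknown.

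**What to change.** Reconcile the two sections. Relabel the second index column as the index after prone positioning, or add such a column and keep the before-prone column only if that value is also wanted.

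Three smaller changes would help and are optional:

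- Record the time of the after-prone reading, so that its timing can be checked from the form.
- Use one name for the index, SpO2 or SaO2, in Specific objectives, the Independent variable table, Statistical analysis and the form.
- Code the after-prone cell as not applicable for never-proned patients. The Elimination criteria remove files with incomplete data, and a blank cell could be misread as incomplete.

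The cost is one relabelled or added column and, if wanted, one time field, taken from files that are being reviewed anyway. The drawbacks are slightly more abstraction work and a second look at any proned patients' files already abstracted under the printed header. Some of those files may prove to lack a post-prone value.
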